8.5.1.3 Bioanalytic method

Serum PK and ADA samples will be assayed using validated methods as described in [Table 4](#).

Table 4 - Summary of bioanalytical methods for functional dupilumab and anti-dupilumab antibodies

Note: In the event of any SAE, any AE of severe injection site reaction lasting longer than 24 hours, or any AESI of anaphylactic reaction or systemic allergic reaction that is related to IMP and require treatment, PK and ADA samples will be collected at or near the onset of the event for

any additional analysis if required or for archival purposes. The exact date and time of sample collection must be recorded and entered into the database by the central laboratory. An unscheduled systemic drug concentration page in the eCRF must be completed as well. If necessary for safety monitoring, additional PK and ADA samples may be collected after the EOS Visit until resolution of AE.

Specifically for PK, any changes in the timing or addition of time points for any planned study assessments must be documented and approved by the relevant study team member and then archived in the Sponsor and site study files, but will not constitute a protocol amendment. The IRB/IEC will be informed of any safety issues that require alteration of the safety monitoring scheme or amendment of the ICF.

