Anaphylactic reaction	Anaphylactic reaction algorithmic approach (Introductory Guide for Standardised MedDRA Queries (SMQs) Version 18.1): includes anaphylactic reaction narrow SMQ (20000021) terms and programmatic identification of cases based on occurrence of at least two preferred terms meeting the algorithm criteria occurring within 24 hours of each other. The latter cases identified using the algorithm will undergo blinded medical review taking into account the timing of events relative to each other and to IMP administration for final determination of an anaphylactic reaction or not.
Systemic hypersensitivity reactions	SMQ [20000214] hypersensitivity narrow search and [AE corrective treatment/therapy='Y' or Action taken with IMP='Drug withdrawn' or Action taken with IMP='Drug interrupted'] followed by blinded medical review (documented process) for selection of relevant systemic hypersensitivity events
Helminthic infections	CMQ10544 based on HLGT as "Helminthic disorder"
Any severe type of conjunctivitis	CMQ10498 based on PTs (See Section 5.6) ^a and "Severe" ticked in Adverse Events eCRF page
Any severe type of blepharitis	CMQ10497 based on HLGT as "Lid, lash and lacrimal infections, irritations and inflammations" and "Severe" ticked in Adverse Events eCRF page
Keratitis	CMQ10642 based on the following PTs [keratitis, allergic keratitis, ulcerative keratitis, atopic keratoconjunctivitis, herpes ophthalmic, ophthalmic herpes simplex, corneal infection] ^a
Clinically symptomatic eosinophilia (or eosinophilia associated with clinical symptoms) ^b	CMQ10641 based on HLGT = Eosinophilic disorders or PT=Eosinophil count increased

AE Grouping	Criteria
Pregnancy of a female participants entered in a study as well as pregnancy occurring in a female partner of a male participant entered in a study with IMP/NIMP	“Pregnancy” or “Partner Pregnancy” checked on the Pregnancy eCRF page as reported by the investigator
Significant ALT elevation	“ALT increase” and AESI answer “Yes” checked on AE eCRF as reported by the investigator (ALT >5 x ULN in participants with baseline ALT ≤2 x ULN; OR ALT >8 x ULN if baseline ALT >2 x ULN)
Symptomatic overdose with IMP	Symptomatic Overdose is answered Yes, with Overdose of IMP answered Yes on AE eCRF.
Symptomatic overdose with NIMP	Symptomatic Overdose is answered Yes, with Overdose of NIMP answered Yes on AE eCRF.
Other selected AE Grouping	

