Serious injection site reactions or severe injection site reactions that last longer than 24 hours	HLT = ‘Injection site reaction’ and either with serious status, or with severe status and (AE end date/time - AE start date/time) ≥24 hours or ongoing
Severe or serious infection	Primary SOC = ‘Infections and infestations’ and with severe or serious status
Drug-related hepatic disorder	SMQ [20000006] Drug-related hepatic disorders- narrow
Injection site reaction	HLT = ‘Injection site reaction’
Malignancy	SMQ [20000091]- Malignant or unspecified tumors narrow
Suicidal behavior	CMQ10639 based on the following PTs [Completed suicide, Suicidal ideation, Depression suicidal, Suicidal behavior, Suicide attempt] ^a
Conjunctivitis (narrow)	CMQ10644 based on the following PTs [Conjunctivitis, Conjunctivitis allergic, Conjunctivitis bacterial, Conjunctivitis viral, Atopic keratoconjunctivitis] ^a
Conjunctivitis (broad)	CMQ10645 based on the following PTs [Conjunctivitis, Conjunctivitis allergic, Conjunctivitis bacterial, Conjunctivitis viral, Atopic keratoconjunctivitis, Blepharitis, Dry eye, Eye irritation, Eye pruritus, Lacrimation increased, Eye discharge, Foreign body sensation in eyes, Photophobia, Xerophthalmia, Ocular hyperaemia, Conjunctival hyperaemia] ^a
Conjunctivitis (FDA) ^c	CMQ10643 based on the following PTs [Conjunctivitis, Conjunctivitis allergic, Conjunctivitis bacterial, Conjunctivitis viral, Eye irritation, Eye inflammation, Giant papillary conjunctivitis] ^a
Keratitis (FDA) ^c	CMQ30102 based on the following PTs in (keratitis, ulcerative keratitis, allergic keratitis, atopic keratoconjunctivitis, and ophthalmic herpes simplex)

a The list of terms may be adjusted according to MedDRA version changes

b All cases of Eosinophilia will be included in the analysis, where cases associated with clinical symptoms will be further described in the CSR

c FDA requested for US labeling

The following summaries will be provided:

- All TEAEs, by selected standardized MedDRA query (SMQ)/Customized MedDRA query (CMQ) and PT or by laboratory values (as in alanine aminotransferase (ALT) elevation), showing the number (%) of participants with at least 1 PT,
- For each AESI and other selected AE groupings,
 - Number (%) of participants with any specific TEAE
 - Number (%) of participants with any specific serious AE (regardless of treatment emergent status)
 - Number (%) of participants with any specific treatment emergent serious AE

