- The summary statistics (including number, median, Q1, Q3, minimum and maximum) of the peak post-baseline titer for participants with treatment-boosted ADA
- The summary statistics (including number, mean, SD, median, Q1, Q3, minimum and maximum) of the ratio of peak post-baseline titer to baseline titer for participants with treatment-boosted ADA
- Listing of ADA peak titer levels and neutralizing antibody status
- Number (%) of participants with neutralizing antibody status.

Kinetics of treatment-emergent ADA response

Number (%) of participants with treatment-emergent ADA positive response at each visit will be summarized, including titer categories (lower, moderate, and high titer), by each intervention group.

A plot of percentage of participants with treatment-emergent ADA positive response at each visit will be provided by each intervention group.

Association of Immunogenicity with Exposure, Safety and Efficacy

The safety and efficacy analyses mentioned below will be conducted using the following categories:

- ADA positive participants: Participants with treatment-emergent or treatment-boosted response.
- ADA negative participants: Participants with pre-existing immunoreactivity or negative in the ADA assay at all time points.

Association of ADA with PK

Associations between ADA variables (eg, ADA peak titers, neutralizing antibody status, treatment-emergent, persistent, indeterminate and transient response, treatment-boosted) and concentration of dupilumab in serum may be explored for each dupilumab dose group. A plot of

concentration of functional dupilumab versus visit will be provided by ADA classifications for the dupilumab dose group. Individual participant plots of dupilumab concentration according to ADA status will be provided to assess the impact of ADA on PK.

Association of ADA with clinical efficacy endpoints

Associations between the ADA variables (eg, ADA peak titers, neutralizing antibody status, treatment-emergent, persistent and treatment-boosted) and the primary efficacy endpoint may be explored for the dupilumab dosed group.

Association of ADA with clinical safety endpoints

Association of safety versus ADA status may be analyzed in the ADA population. The safety assessment may focus on the following events:

- Severe injection site reactions last longer than 24 hours or serious injection site reactions
- Hypersensitivity reactions (SMQ (20000214) hypersensitivity narrow search confirmed by medical review)

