- Anaphylactic reactions (SMQ (20000021) anaphylactic reaction narrow search)

Associations between ADA variables (eg, ADA peak titers, neutralizing antibody status, treatment-emergent, persistent and treatment-boosted) and safety may be explored.

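### SAP 4.8.2 defines anaphylaxis for the optional ADA-safety analysis by the narrow SMQ alone, so a case confirmed only through the SAP Table 8 algorithm is left out of that category

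*SAP*

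**What the plan says.** Table 8 in SAP 4.7.2 selects anaphylactic reactions in two ways. The first is any term in narrow SMQ 20000021. The second is "programmatic identification of cases based on occurrence of at least two preferred terms meeting the algorithm criteria occurring within 24 hours of each other". For the second set it adds: "The latter cases identified using the algorithm will undergo blinded medical review". That review takes account of the timing of the events relative to each other and to dosing, and it decides whether each case is anaphylaxis.

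SAP 4.8.2, under the association of ADA with clinical safety endpoints, opens permissively: "Association of safety versus ADA status may be analyzed in the ADA population". It then names three kinds of event on which the assessment may focus:

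- The first line concerns the injection site and reads "Severe injection site reactions last longer than 24 hours or serious injection site reactions".
- The second line concerns allergic events more broadly and reads "Hypersensitivity reactions (SMQ (20000214) hypersensitivity narrow search confirmed by medical review".
- The third line concerns anaphylaxis and reads "Anaphylactic reactions (SMQ (20000021) anaphylactic reaction narrow search".

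The anaphylaxis line mentions neither the algorithm nor medical review, and it does not point to Table 8.

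**The concern.** The same SAP has two definitions of one event, and the narrower one is in the analysis that relates the event to immunogenicity. Protocol 2.3 calls systemic hypersensitivity an important identified risk, describes monoclonal antibodies as potentially immunogenic, and reports dupilumab-related anaphylaxis in adult asthma trials. If an ADA-by-anaphylaxis display is produced, it should therefore use the adjudicated cases.

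The algorithm exists to find cases recorded as separate signs rather than under one diagnostic term. Protocol Appendix 8 (10.8) itself defines anaphylaxis by combinations of signs across organ systems. A case that blinded review has accepted on that basis would appear in the ADA display as a participant without anaphylaxis.

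**Working it through.** The plan states no figure on this point, so the check compares the definitions.

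**The two anaphylaxis definitions.** Let N be a hit on narrow SMQ 20000021, and let A be an algorithm case confirmed by blinded review.

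- SAP Table 8: anaphylaxis = N or A.
- SAP 4.8.2: anaphylaxis = N.
- Difference: A and not N, which is a case confirmed only through the algorithm.

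The 4.8.2 wording cannot safely be read as shorthand for both routes. Table 8 treats the narrow terms and the algorithm cases as separate sets and sends only the second to review. A programmer who follows 4.8.2 literally would build N.

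**The neighbouring lines in 4.8.2.** These show whether the narrowing looks deliberate.

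- Injection site reactions: the 4.8.2 line restates the Table 8 row, "Serious injection site reactions or severe injection site reactions that last longer than 24 hours".
- Hypersensitivity: the 4.8.2 line keeps medical review and applies no filter on treatment or on action taken with study drug.
- Anaphylaxis: this is the only line that loses a reviewed route. The SAP gives no reason, so an oversight is the likelier explanation.

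**Where an affected case still appears.** It stays in the Table 8 anaphylaxis count. It also enters the 4.8.2 hypersensitivity category if one of its terms is in narrow SMQ 20000214 and review confirms it. The documents do not reproduce the SMQ term lists or the algorithm criteria, so the overlap cannot be measured.

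**Scale per case.** About 75 participants are planned per arm (Protocol 9.2).

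- One case is 1/75 = 1.3 percentage points.
- Exact 95% intervals are 0 to 4.8% for 0/75 and 0.03 to 7.2% for 1/75, so they largely overlap.
- The ADA population needs a post-dose ADA result (SAP Table 4), and scheduled ADA samples are not taken in China (Protocol 10.10), so the denominator may be smaller. At an assumed 60 per arm, one case is 1/60 = 1.7 points.

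These figures give the weight of any single misclassified participant. They do not estimate how many there will be. The ADA-positive rate is not given, so no effect within ADA-positive participants can be computed.

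**The case against.** The strongest reply is that little depends on this line. The analysis is optional in both documents (Protocol 9.4.3 and SAP 4.8.2). The event list is only a suggested focus, and 4.8.2 closes by allowing ADA variables to be explored against safety in general. Nothing bars an algorithm-confirmed case from that exploration. Protocol 10.3 also asks sites to record the diagnosis rather than individual signs where possible, so algorithm-only cases should be uncommon. All of this stands, and it keeps the point minor. It does not justify the narrower definition: if the named display is produced as written, an adjudicated case is mislabelled.

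A reader might draw stronger conclusions that the documents do not support:

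- **That the report would contradict itself on the number of anaphylaxis cases.** Table 8 uses the safety population and the ADA display uses the ADA population. The two counts could differ even with identical definitions.
- **That ADA samples taken at onset would go unused.** The protocol says "PK and ADA samples will be collected at or near the onset of the event", but for further analysis if required or for archiving. It does not say that these samples feed the display. The participant also keeps an ADA status and stays in the denominator; only the anaphylaxis label is missing.
- **That the hypersensitivity definitions are also at fault.** The Table 8 row admits events with corrective treatment, or with study drug withdrawn or interrupted. This is a defensible case definition, in line with the protocol's references to systemic allergic reactions that require treatment (7.1.1, 8.3 and 8.5.1.3). Serious events outside it remain in the serious adverse event tables, and investigator-flagged events are summarized separately. Widening the row would be a preference, not a correction.

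**Conclusion.** The inconsistency is real and minor. Followed as written, SAP 4.8.2 would show a participant whose anaphylaxis was confirmed only through the Table 8 algorithm as having no anaphylaxis in the ADA-safety display. This assumes that the optional analysis is run and that the line is programmed literally. The number of such cases is not given; zero to a few is a judgement, based on the recording instruction in Protocol 10.3.

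The effect is confined to one descriptive cross-tabulation. SAP 4.7 plans no testing of safety variables, and the hierarchy in SAP 4.6 contains no safety or ADA item. No efficacy result or tested conclusion changes, the main Table 8 count is complete, and there is no basis for claiming bias between arms.

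**What to change.** In SAP 4.8.2, replace the anaphylaxis line with:

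> Anaphylactic reactions as selected in Table 8 (narrow SMQ 20000021 terms and algorithm cases confirmed by blinded medical review)

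Leave the other two lines, and Table 8 itself, as they are. The change is one cross-reference made before database lock. It needs no new data and no extra review, because Table 8 already requires the adjudication.

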4.8.3 Pharmacodynamic/genomics endpoints

Venous blood samples will be collected at Visit 2 (Week 0), Visit 3 (Week 4), Visit 4 (Week 8), Visit 5 (Week 12), Visit 6 (Week 24), and Visit 7 (Week 36), for measurement of total serum IgE. Total IgE will be measured using validated quantitative methods.

For those participants who consent to the optional pharmacogenetic/pharmacogenomic sample collection section of the ICF, blood (serum/plasma) for possible future analysis of potential biomarkers of drug response, disease activity, safety, and the Type 2 inflammation pathway, and blood samples for exploratory genetic analysis of DNA or RNA will be collected and stored for possible future use. Participation is optional. Participants who do not wish to participate in the genetic research may still participate in the study.

For the optional skin biopsy (substudy), the sample will be taken from lesion and non-lesion skin using punch biopsy.

Total IgE will be summarized in the safety population defined as participants who actually received at least 1 dose or part of a dose of the IMP. Baseline values will be the last value collected prior to the first IMP. Descriptive statistics (including number, mean, SD, median, Q1, Q3, min, max) of biomarkers at baseline will be summarized. In addition, for participants who take the prohibited medications/procedures or rescue medications defined in [Table 5](#), the data after the medications will be censored and then last observation carried forward (LOCF) method will be implemented for missing data imputation in the analysis.

Summary plots (median with interquartile range) on values at each visit, absolute changes from baseline and percent changes from baseline will be provided for the total IgE by intervention group and visit.

Exploratory analysis of DNA, RNA and urine biomarkers will be addressed in a separate document.

The analyses of the skin biopsy substudy will be addressed in a separate document.

4.9 INTERIM ANALYSES

No interim analysis is planned.

A primary database lock will be performed when all randomized participants in this study have completed their 24-week treatment phase. Final analyses in the CSR will be based on this database.

The database will be updated at the end of the study for all participants to include the post-treatment follow-up information and updates for the events previously ongoing at the time of the primary lock. Additional data between this database lock and last participant completing last visit will be summarized in a CSR addendum.

5 SUPPORTING DOCUMENTATION

5.1 APPENDIX 1 LIST OF ABBREVIATIONS

ADA:	anti-drug antibody
AE:	adverse event
AESIs:	adverse events of special interest
ALT:	alanine aminotransferase
ANCOVA:	analysis of covariance
AST:	aspartate aminotransferase
ATC:	anatomic category
CDG:	company drug grouping
CI:	confidence interval
CLcr:	Creatinine clearance
CMH:	Cochran-Mantel Haenszel
CSR:	clinical study report
DLQI:	Dermatology Life Quality Index
DNA:	deoxyribonucleic acid
ECG:	electrocardiogram
eCRF:	electronic case report form
EMA:	European Medicines Agency
EOT:	end of treatment
EQ-5D:	Euroqol 5 dimensions
EQ-5D-5L:	5-level EuroQol 5-dimensional questionnaire
FDA:	Food and Drug Administration
HADS:	hospital anxiety and depression scale
HBc Ab:	hepatitis B core antibody
HBs Ab:	hepatitis B surface antibody
HBs Ag:	hepatitis B surface antigen
HBV:	hepatitis B virus
HCV Ab:	hepatitis C virus antibodies
HGLT:	high level group term
HLT:	high level term
HRQoL:	health-related quality-of-life
IGA PN:	Investigator's global assessment for prurigo nodularis
IGA PN-A:	IGA PN-Activity
IGA PN-S:	IGA PN-Stage
IMP:	investigational medicinal product
ITT:	intent-to-treat
LLT:	lower-level term
LS:	least squares
MedDRA:	medical dictionary for regulatory activities
NRS:	numeric rating scale
PCSA:	potentially clinically significant abnormality

PD:	pharmacodynamic
PGIC:	Participant Global Impression of Change
PGIS:	Participant Global Impression of Severity
PK:	pharmacokinetic
PN:	prurigo nodularis
PT:	preferred term
RNA:	ribonucleic acid
SAE:	serious adverse event
SAP:	statistical analysis plan
SD:	standard deviation
SDG:	standardized drug grouping
SMQ:	standardized MedDRA query
SOC:	system organ class
TEAE:	treatment-emergent adverse event
ULN:	upper limit of normal
VAS:	visual analog scale, visual analog scale
WHO-DD:	World Health Organization-Drug Dictionary
WI-NRS:	worst-itch numeric rating scale
WOCF:	worst-observation carried forward

5.2 APPENDIX 2 CHANGES TO PROTOCOL-PLANNED ANALYSES

This section summarizes major statistical changes in the protocol amendments. As mentioned previously, the Sponsor made the decision to complete the study as originally planned instead of resizing the study based on the results of EFC16460 after a health authority's feedback on Protocol Amendment 2 dated 14-Apr-2021.

Table 9 - Major statistical changes in protocol amendment(s)

Amendment Number	Approval Date	Changes	Rationale
1	20-May-2020	To add "proportion of participants with Investigator's Global Assessment 0 or 1 score for PN-Stage (IGA PN-S) at Week 24" as another key secondary endpoint	To include a lesion-related key secondary endpoint according to the health authority's recommendations
		To remove the endpoint "Change from baseline in PAS total score at Week 4, Week 8, Week 12, and Week 24" in the exploratory endpoint and modify the exploratory endpoint regarding the healed lesions from PAS questionnaire analysis	To clarify the analysis on efficacy evaluation of dupilumab on skin lesions using a modified prurigo activity score (PAS) 5-item questionnaire
		To break out the secondary endpoints with multiple measuring timepoints into individual endpoints.	To clearly define the timepoints of each endpoint according to health authority's recommendation

Amendment Number	Approval Date	Changes	Rationale
		To add the sensitivity analysis for secondary endpoints information, and to separate key secondary endpoints in a different row	To evaluate the robustness of the missing data imputation assumption by sensitivity analyses, and to clarify the endpoints analyses
		To add the covariate "baseline anti-depressant use (yes or no)" to primary and secondary endpoint analyses	To adjust for potential impact of anti-depressant use on the treatment effect in primary and secondary efficacy analyses
		The following wording was added: "Data collected regarding the impact of the COVID-19 or other pandemics, on the participants will be summarized (eg, discontinuation due to COVID-19). Any additional analyses and methods required to investigate the impact of COVID-19 or other pandemics requiring public health emergency on the efficacy (eg, missing data due to COVID-19) and safety will be detailed in the SAP".	To describe alternative temporary mechanism that can be implemented in the study conduct in case of pandemic requiring public health emergency eg, COVID-19
2	14-Apr-2021	
Added 2 more populations for analyses in the case an earlier primary database lock occurs.
 
The ITT-Week-12 population consists of all participants who had been randomized by 14 June 2021.
 
The ITT-Week-24 population consists of all participants who had been randomized by 22 March 2021.
	To detail how the endpoints will be analyzed in the case of an early primary database lock. Based on the timing of the availability of the EFC16460 results, and to ensure a minimum of 135 participants have the opportunity to reach the Week 24 endpoint, the randomization cut-off dates have been assessed as 22 March 2021 for Week 24 and 14 June 2021 for Week 12.
		
Added text:
 
The analysis population for the efficacy endpoints will be the ITT population. In the case of an early primary database lock prior to the last enrolled participant reaching EOT, the analysis population will be the ITT-Week-12 population for endpoints which occur earlier than or equal to Week 12. The ITT-Week-12 population consists of all participants who had been randomized by 14 June 2021. The analysis population for Week 24 endpoints will be the ITT-Week-24 population. The ITT-Week-24 population consists of all participants who had been randomized by 22 March 2021.
 
Modification in accordance with the above proposal will be documented in the SAP prior to the database lock.
	To provide detail of how data from timepoint evaluations will be handled in the case of an early primary database lock.

Amendment Number	Approval Date	Changes	Rationale
		
Added text:
 
In the case of an early primary database lock prior to the last enrolled participant reaching EOT, the analysis of safety will be performed on all available and safety data collected up to the time of the primary database lock.
 
Added text in Table 7:
 
In addition, exposure-adjusted AE incidence rate tables will present by SOC and PT the number of patients with at least 1 event per 100 patient-years.
	With an early primary analysis, participants may have different treatment exposure because of study design.
3	21-Oct-2021	
To promote the “proportion of participants with improvement (reduction) in worst-itch numeric rating scale (WI-NRS) by ≥ 4 from baseline to Week 24 as primary endpoint and to move the “proportion of participants with improvement (reduction) in WI-NRS by ≥ 4 from baseline to Week 12” to a secondary endpoint
	Based on the data from EFC16460, the treatment effect of dupilumab continued to improve over time through Week 24. Therefore, the Sponsor proposes to assess the proportion of participants with improvement (reduction) in WI-NRS by ≥ 4 at Week 24, which represents the effect more accurately and synchronizes the primary itch assessment with the primary lesion assessment
		
To update the sample size calculation based on the observed effect sizes from EFC16460.
	To assess a timepoint that reflects the optimal dupilumab treatment effect as a primary endpoint
		
To update the primary analysis considerations to the Week 24 timepoint.
	To be consistent with primary endpoint change
		
To remove the sentence “A key secondary endpoint will be the responder analyses of itch improvement of at least 4 points at Week 24.” as it is now the primary endpoint, and to provide rationale for choosing the primary endpoint timepoint at Week 24 with the following language: “The timing of the primary assessment, ie, at Week 24, was based on the results of the primary analysis of EFC16460, showing that the effect of dupilumab over time showed continuous improvement after Week 12 across all endpoints, with a similar time course of improvement in both itch and lesion endpoints through at least Week 24. Since improvement of itch and lesions may occur prior to Week 24, responder analyses assessments will be performed at earlier time points as well, starting at Week 2 for itch, and Week 4 for lesions.”
	To provide rationale and maintain consistency in language with the change in the primary endpoint.

Amendment Number	Approval Date	Changes	Rationale
		To specify that the rationale for a 24-week duration of the trial is an appropriate duration based on data observed from EFC16460 and to remove references to atopic dermatitis trials.	To reflect that data from EFC16460 has informed our understanding of the dupilumab treatment effect continuing to improve itch through Week 24. The Week 24 timepoint most accurately represents the overall treatment effect and synchronizes the primary itch assessment with the primary lesion assessment.
		To reflect that the primary endpoint timepoint is Week 24.	To maintain consistency in language with the change in the primary endpoint.
		To update Table 6 to reflect that the primary endpoint is assessed at Week 24.	To maintain consistency in language with the change in the primary endpoint.
		To remove the possibility of re-evaluating the timing of the primary database lock of EFC16459 based on the observed treatment effect size in EFC16460, that was added per Amendment 02. And to consequently remove the 2 populations (ITT-Week 12 and ITT-Week 24) that were added per Amendment 02.	Amended protocol 02 was submitted in few countries but was withdrawn following a Health Authority feedback and was not implemented in any country.
		Subsection 10.12.2 was added and the overall rationale and table with summary of changes for Amended protocol 02 were moved from the cover page to this section.	This is aligned with Sanofi procedures.

5.3 APPENDIX 3 DEMOGRAPHICS AND BASELINE CHARACTERISTICS, PRIOR OR CONCOMITANT MEDICATIONS/PROCEDURES

Demographics, baseline characteristics, medical surgical history

The following demographics and baseline characteristics, medical and surgical history and disease characteristics at baseline will be summarized using descriptive statistics in the randomized population.

Demographic variables are

- Age in years (quantitative and qualitative variable: 18-<40, 40-<65, 65-<75, and ≥ 75 years),
- Gender (Male, Female),
- Race (White, Black or African American, Asian, American Indian or Alaska Native, Native Hawaiian or other Pacific Island, unknown),
- Ethnicity (Hispanic or Latino, Not Hispanic or Latino, Unknown),
- Region (Asia: Japan, China, South Korea; East Europe: Russia; Latin America: Argentina, Mexico; Western Countries: USA, France),

- Territory (North America: USA; European Union: France; Rest of World: Russia, Japan, China, South Korea, Argentina, Mexico),
- Weight in kg (quantitative and qualitative variable: (<60, \geq 60- <90, \geq 90 kg),
- BMI in kg/m² (quantitative and qualitative variable: (<25, \geq 25- <30, \geq 30 kg/m²).

Baseline safety and efficacy parameters (apart from those listed above) will be presented along with the safety and efficacy summaries.

Medical (or surgical) history includes all the relevant medical (or surgical) history during the lifetime of the participant.

This information will be coded using the version of MedDRA currently in effect at Sanofi at the time of database lock.

Comorbidity will be summarized separately. The following comorbid diseases will be summarized from electronic case report form (eCRF) pages which were filled in by investigators based on participant reporting.

- Prurigo nodularis (Yes, Ongoing condition)
- Atopic dermatitis (Yes, Ongoing condition)
- Allergic rhinitis history (Yes, Ongoing condition)
- Allergic rhinoconjunctivitis (Yes, Ongoing condition)
- Asthma history (Yes, Ongoing condition)
- Food allergy history (Yes, Ongoing condition)
- Eosinophilic esophagitis history (Yes, Ongoing condition).

Disease characteristics at baseline

The following baseline disease characteristics will be summarized by intervention group:

- Duration of PN and grouping (years; <3 and \geq 3) to be derived as
 - (Year of randomization – Year of first diagnosis of PN) + (month of randomization - month of first diagnosis of PN)/12
- Age of onset of PN (years)
- History of atopy (atopic or non-atopic)
 - Number of mild AD participants under atopic
- Stable use of TCS/TCI (yes or no)
- Baseline WI-NRS score
- Baseline IGA PN-S score (summary and frequency by each score level)
- Baseline IGA PN-A score (summary and frequency by each score level)

- Baseline skin Pain-NRS score
- Baseline Sleep-NRS score
- Baseline PGIS score
- PAS (number of prurigo lesions in a total and in representative area, and healed prurigo lesions) at baseline
- Baseline Hospital Anxiety and Depression Scale (HADS) total score
 - Baseline Hospital Anxiety score
 - Baseline Depression Scale score
- Baseline Dermatology Life Quality Index (DLQI) score
- Baseline EuroQol five dimensions questionnaire (ED-5D-5L) (single index score and VAS)
- Frequency of alcohol drinking in the past 12 months (never, occasional, at least monthly, at least weekly, at least daily) and number of drinks on a typical day (1 or 2, >2)
- Antidepressant use (yes or no) at baseline
- HIV (positive versus negative).

Prior or concomitant medications and procedure

All medications will be coded using the World Health Organization-Drug Dictionary (WHO-DD) using the version currently in effect at Sanofi at the time of database lock.

All procedures will be coded to a PT and associated primary SOC using the version of MedDRA currently in effect at Sanofi at the time of database lock.

- Prior medications/procedures are those the participant used prior to first investigational medicinal product (IMP) injection. Prior medications/procedures can be discontinued before first administration or can be ongoing during treatment phase.
- Concomitant medications/procedures are any interventions received by the participant concomitantly to the IMP, from first administration of IMP to last IMP intake + 98 days.
- Post-treatment medications/procedures are those the participant took in the period running from the end of the concomitant medications period up to the end of the study.
- A given medication/procedure can be classified as a prior medication/procedure and/or as a concomitant medication/procedure and/or as post-treatment medication/procedure. If it cannot be determined whether a given medication/procedure was taken prior or concomitantly or post, it will be considered as prior, concomitant, and post-treatment medication/procedure.

The prior and concomitant medications/procedure will be summarized for the randomized population.

Medications will be summarized by intervention group according to the WHO-DD dictionary, considering the first digit of the anatomic category (ATC) class (anatomic category) and the first 3 digits of the ATC class (therapeutic category). All ATC codes corresponding to a medication will be summarized, and participants will be counted once in each ATC category (anatomic or therapeutic) linked to the medication. Therefore, participants may be counted several time for the same medication.

The table for prior medications will be sorted by decreasing frequency of ATC followed by all other therapeutic classes based on the overall incidence across intervention groups. In case of equal frequency regarding ATCs (anatomic or therapeutic categories), alphabetical order will be used.

Concomitant medication received during first IMP to last IMP +14 days and concomitant medication received during first IMP to last IMP +98 days will be summarized separately. The tables for concomitant medications will be sorted by decreasing frequency of ATC followed by all other therapeutic classes based on the incidence in the dupilumab group. In case of equal frequency regarding ATCs (anatomic or therapeutic categories), alphabetical order will be used.

Medications will also be summarized by generic name sorted by decreasing frequency based on the incidence in the dupilumab group.

Procedures will be summarized by intervention group by primary SOC (sorted by internationally agreed order) and PT (sorted in alphabetical order), sorting is based on the overall incidence across intervention groups.

Background intervention

Participants will be required to apply moisturizers (emollients) once or twice daily for at least the 7 consecutive days immediately before baseline (Day 1) and continue until Week 36.

The compliance of moisturizers (emollients) used from 7 days before the baseline visit to Week 36 (or end of study), which is defined as the (number of days moisturizers used during the period)/(number of days within the period) x 100%, will be summarized by intervention group.

Similarly, the compliance of moisturizers (emollients) used from the baseline visit to Week 12 and Week 24 will be summarized by intervention group respectively.

In addition, the compliance of use of TCS/TCI from the baseline visit to Week 12 and Week 24 for participants with the stratification of stable use of TCS/TCI (yes) will be summarized by intervention group respectively.

Prohibited medications/procedures

The concomitant use of the following therapies is prohibited during the entire study. Study treatment will need to be discontinued in participants receiving these treatments:

- Systemic immunosuppressive/immunomodulating drugs (eg, systemic corticosteroids, cyclosporine, mycophenolate-mofetil, interferon gamma, Janus kinase inhibitors, azathioprine, methotrexate, hydroxychloroquine, dapson, sulfasalazine, colchicine, etc)
- Other monoclonal antibodies (which are biological modifiers)
- Phototherapy, including tanning beds
- Naltrexone or other opioid antagonist
- Gabapentin, pregabalin, and thalidomide

The concomitant use of the following therapies is prohibited except if the dose has been stable for at least 3 months prior to screening, but study treatment will not need to be discontinued in participants receiving the treatments listed below. The dose should also remain stable (can be reduced or discontinued if medically indicated) and should not be increased during the study.

- Paroxetine, fluvoxamine, or other SSRIs
- SNRIs
- Amitriptyline or other tricyclic or tetracyclic antidepressants

The concomitant use of the following therapies is also prohibited during the entire study, but study treatment will not need to be discontinued in participants receiving the treatments listed below:

- Intralesional corticosteroid injections and cryotherapy
- Sedating antihistamine
- Non-sedating antihistamine if used specifically for the treatment of itch secondary to AD or PN.

The number and percentage of participants who take the prohibited medications/procedures will be provided. In addition, the time (week) of first prohibited medication/procedure taken will also be analyzed using Kaplan-Meier method.

Rescue medications

The following rescue medications may be used:

- Dermatological preparations of high potency or superpotent TCS and TCI.

If medically necessary (ie, to control intolerable PN symptoms), rescue treatment for PN may be provided to study participants at the discretion of the Investigator.

Although the use of rescue medications is allowed at any time during the study, the use of rescue medications should be delayed, if possible, for at least 14 days following the initiation of the investigational treatment. The date and time of rescue medication administration as well as the name and dosage regimen of the rescue medication must be recorded in the eCRF.

- For the purpose of the efficacy responder analysis, a pre-specified algorithm will be used to classify rescue. In addition, a blinded review of all post-baseline medications to adjudicate rescue treatment, based on medical judgment, will be performed to adjudicate rescue. Participants who receive rescue treatment as per this adjudication during the study will be considered treatment failures.

The rescue medications will be analyzed by the same method as that used for prohibited medications/procedures.

